| LSN : | Upper Normal Limit |
| WHO : | World Health Organization |
| RECISTm : | RECIST Modified |
| TACE: | Transarterial chemoembolization |
| TSH | Thyroid Stimulin |
| AFP | Alpha Foeto Protein |

3 Introduction

3.1 Rationale for the study

Transarterial chemoembolization (TACE) is a commonly used technique in the treatment of patients with isolated or small hepatocellular carcinoma not amenable to surgical resection (intermediate stage), with an advantage in terms of survival time over symptomatic treatments. This approach is justified by the fact that HCC is a highly vascularized tumor, with a major role of angiogenesis.

Sunitinib is a novel multi-targeted tyrosine kinase inhibitor with both angiogenesis inhibition and direct anti-tumor properties. The addition of sunitinib may therefore reduce the risk of tumor recurrence in HCC patients treated with TACE. Nevertheless, some angiogenesis inhibitors are associated with an increased risk of bleeding complications, which may raise concerns about their use in patients with HCC. Thus, it is important to evaluate the safety of the sunitinib-chimioembolization combination, and compare it to chemoembolization alone (chemoembolization plus placebo).

3.2 Objectives

3.2.1 Pilot phase

To assess the rate of bleeding and/or severe liver failure within one week of chemoembolization sessions in patients receiving sunitinib.

3.2.2 Phase II

3.2.2.1 Main objective

Assess the rate of bleeding and/or severe liver failure within one week of chemoembolization sessions.

3.2.2.2 Secondary objectives

The secondary objectives of the phase II study are to evaluate:

- tumor control rate* at 3, 6, 9 months after the last TACE ;
- Progression-free survival
- Overall survival*;
- Tolerance*;
- Quality of life*.

*These objectives are common objectives with la phase III

3.2.3 Phase III

3.2.3.1 Main objective

Compare overall survival in the sunitinib and placebo groups.

3.2.3.2 Secondary objectives

- The common criteria between la Phase II and la Phase III are described in Section 3.2.2.2 (marked with an *).
- Disease-free survival

4 Study population

4.1 Inclusion criteria

- Histologically proven hepatocellular carcinoma (HCC) or liver tumor meeting the Barcelona criteria.
- Child-Pugh A score.
- Tumor not accessible to surgical resection or radiofrequency.
- Tumor undergoing transarterial chemoembolization (TACE).
- Age \geq 18 years.
- Performance Index (WHO) \leq 2.
- A previous radiofrequency treatment is allowed if it took place more than 3 months before.
- Satisfactory hematologic, renal, and hepatic function (neutrophils \geq 1.5 \times 10⁹/L, platelets \geq 70 \times 10⁹/L, hemoglobin \geq 10 g/dL, prothrombin time \geq 50%, creatinine level \leq 120 μ mol/L, bilirubin level (\leq 15 mg/L), alanine and aspartate transaminases (ALAT and ASAT) \leq 4 times the upper limit of normal (ULN), alkaline phosphatases \leq 5 times ULN, and fibrinogen level \geq 1.5 g/L.
- Signed written consent.

4.2 Non-inclusion criteria

- History of chemoembolization.
- Portal thrombosis.
- Extra-hepatic metastases including brain metastases.
- Uncontrolled hypertension or requiring at least 2 classes of antihypertensive agents (uncontrolled hypertension (systolic pressure $>$ 160 mmHg, diastolic pressure $>$ 100 mmHg) well-conducted antihypertensive treatment)
- Uncontrolled heart failure (left LVEF $<$ 50%) or coronary artery disease, recent myocardial infarction (less than one year), QT interval prolongation $>$ 450 ms in men and $>$ 470 ms in women.
- Concomitant disease or severe uncontrolled clinical situation.
- Uncontrolled severe infection.
- Patient treated with a CYP3A4 inhibitor within 7 days prior to treatment.
- Patient treated with a CYP3A4 potentiator within 12 days.
- Patients requiring long-term anticoagulant treatment.
- Pregnancy or breastfeeding.
- Lack of effective contraception (for men or women of childbearing age).
- Prior treatment with sunitinib, sorafenib or other angiogenesis inhibitors.
- History of other cancers excluding cancers known to be cured for more than 5 years (in this case histological evidence of HCC is required), or basal cell skin tumors or cervical cancer in situ adequately treated with curative intent.
- Patient who for psychological, social, family or geographical reasons could not be followed regularly.
- Concurrent participation of the patient in another experiment.
- Patient with a contraindication to vascular occlusion procedures.
 - Vascular anatomy that precludes catheterization or injection of emboli.
 - Presence or likely onset of vasospasm.

- Presence or probable occurrence of a hemorrhage.
- Presence of severe atheromatous damage.
- Presence of feeder arteries smaller than the distal branches from which they emerge.
- Presence of extra to intracranial anastomoses or patent shunts.
- Presence of collateral vascular pathways potentially endangering normal territories during embolization.
- Presence of terminal arteries leading directly to the cranial nerves.
- Presence of arteries irrigating the lesion not wide enough to receive the microbeads.
- Peripheral vascular resistance of the feeding arteries excluding the passage of microbeads into the lesion.
- Do not use microbeads in the following applications:
 - embolization of non-malignant tumors;
 - embolization of large-diameter arteriovenous shunts (i.e., where the blood does not pass through the arterial/capillary/venous transition but goes directly from the artery to the vein);
 - any vascular system where the microbead embolic agent is CN00103.2 likely to pass directly into the internal carotid artery or other non-target territory.

5 Experimental design

5.1 Scheme of the study

The study is a phase II-III, parallel-group, multicenter study.

5.2 Study arms

- Arm A: chemoembolization plus sunitinib.
- Arm B: chemoembolization plus placebo.

5.3 Randomization and blinding

The study is double-blind for sunitinib or placebo (neither the doctor nor the patient knows which treatment is being given).

Stratification by minimization is performed, starting in la phase II, on:

[figure not shown]
- diameter of the primary tumor (< 5 versus \geq 5 cm)
- the presence of one nodule versus the presence of more than one nodule;
- the investigating center.

When a stratified analysis will be performed, it will be performed only according to the diameter of the main tumor and the number of nodules, according to 4 groups:

[figure not shown]
- diameter < 5 cm and a nodule,
- diameter \geq 5 cm and a nodule,
- diameter < 5 cm and more than one nodule,
- diameter \geq 5 cm and more than one nodule.

5.4 Chronological sequence

The chronological sequence for a patient is described in the following graph:

The study design is as follows:

5.5 Justification of the number of subjects needed

5.5.1 Pilot phase

A non-randomized pilot phase was performed on 10 chemoembolizations performed with sunitinib (regardless of the number of patients included). An independent committee ruled on the safety data for continuation or not in phase II and a specific report was sent to the ANSM for information.

5.5.2 Phase II

The assumptions for calculating the number of subjects needed are:

- H_0 : A rate of bleeding and/or severe liver failure occurring within one week of the chemoembolization session of 30% is considered unacceptable;
- H_1 : A rate of bleeding and/or severe liver failure occurring in the week following the chemoembolization session of less than 30% is necessary to consider the treatment non-toxic; a rate of 15% is expected.

To achieve 85% power (assuming a 15% rate of severe bleeding and/or liver failure), with a two-sided first-step risk of 13.3%, 35 patients per arm are required (in a one-step Fleming design).

5.5.3 Phase III

The assumptions for calculating the number of subjects needed are:

- H_0 : Overall survival in the sunitinib arm is not different from that in the placebo arm; expected 2-year overall survival in the placebo arm is 40%;
- H_1 : Overall survival in the sunitinib arm is different from that in the placebo arm; a 20% difference at 2 years in favor of sunitinib is expected between the two arms (corresponding to a hazard ratio of 0.56).

With a two-sided 5% risk of first-species error, 130 events will be required to achieve 90% power under the previously stated assumption H_1 . Assuming uniform patient inclusion over 2 years, and allowing for a 3-year follow-up after the last inclusion, the number of patients will be 180. To account for a 5% rate of patient attrition, a total of 190 patients will need to be included.

The 70 patients already included in la phase II will be retained for la Phase III, leaving 120 patients to be included.

An interim analysis of the primary endpoint is planned at death 65. This may provide early evidence of superiority of the sunitinib arm. A method of expenditure of the first kind risk (DeMets, 1994), will be used to calculate the nominal values of "p"; this method will make it possible to adjust these threshold values if the intermediate and final analyses are not carried out exactly at the right numbers of events. The expenditure function chosen is an O'Brien function.

Calculations were performed using the R software and the gsDesign library.

| Analysis | Number of events | Nominal value of p | Power to the analysis under hypothesis |
|------------------|------------------|--------------------|--|
| | | | H1 |
| Inter 1 analysis | 65 | 0.0054 | 0.3156 |
| Final analysis | 130 | 0.0439 | 0.5811 |

These values will be adjusted according to the number of actual events at the time of the analyses.

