Two interim analyses are planned to reject H0 or H1. The p value will be done according to East software (Version 5). Using the alpha-spending function (Lan and DeMets, 1983) and O'Brien-Fleming method (O'Brien and Fleming, 1979).

The first interim analysis is planned at the final analysis (9 to 10 months after the inclusion of the first patient) of the phase II study with an expected number of events equal to 10 deaths representing 8 % of the total number of deaths required for the final analysis.

The second interim analysis is planned 34 months after the inclusion of the first patient with an expected number of events equal to 80 deaths representing 2/3 of the total number of deaths required for the final analysis

Overall survival: Time interval between randomization and death (all causes). Alive patients will be censored at the last follow-up

Relapse-free survival: Time interval between randomization and local or distant relapse or death (all causes). Alive patients without relapse will be censored at the last follow-up. Alive patients with secondary cancer will be censored at the last follow-up

Disease-free survival: Time interval between randomization and local or distant relapse or second cancer or death (all causes). Alive patients will be censored at the last follow-up.

An analysis plan will be produced before the database is frozen. All of the analyses will be conducted with a 5% (bilateral) type one error. Analyses of the principal and secondary objectives will be conducted on an intent-to-treat basis and will bear on all of the patients enrolled:

The data for each arm will be presented as means (standard deviation), median and range or percentages and will be compared using the Student t test, Anova or Kruskal Wallis and Wilcoxon for quantitative variables or the Chi 2 and Fisher exact test for qualitative variables.

Median follow up will be calculated according to the so-called « reverse Kaplan Meier » method for each of the Arms, with its 95% confidence interval.

Survival curves will be estimated using the Kaplan-Meier analyses from time to randomization, and compared by the log-rank test and stratified log rank test. Cox proportional hazard models will be used to estimate univariate and multivariate hazard ratios (HR) with 95 % confidence intervals (CI).

The incidence rate of the side effects and of the unexpected serious side effects will be reported using frequencies and percentages for:

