5.6.3.1 Intermediate Analysis

An interim analysis at 65 deaths is planned. This may provide early evidence of superiority of the sunitinib arm.

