7.2.3 Phase III

7.2.3.1 Intermediate Analysis

An interim analysis is planned during la phase III. This analysis is planned at the midpoint of the number of events, i.e. at 65 deaths. Based on the assumptions made, this analysis could take place 28 months after the inclusion of the first patient.

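### SAP 5.5.3: the final p threshold (0.0439) does not pair with the interim threshold (0.0054), the final power entry is an increment, and protocol and SAP plan different interim looks

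*SAP*

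**What the plan says.** SAP 5.5.3 sets a two-sided 5% error, 130 deaths and 90% power for overall survival. It states that "The expenditure function chosen is an O'Brien function" and that the calculations used gsDesign in R. The table has columns for number of events, nominal p, and power at the analysis under H1. Its rows are "Inter 1 analysis | 65 | 0.0054 | 0.3156" and "Final analysis | 130 | 0.0439 | 0.5811". Below it stands: "These values will be adjusted according to the number of actual events at the time of the analyses".

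The SAP repeats the single look in 5.6.3.1 ("An interim analysis at 65 deaths is planned"), where the purpose is early evidence of superiority, and in 7.2.3.1 ("This analysis is planned at the midpoint of the number of events, i.e. at 65 deaths"). The latter adds that "this analysis could take place 28 months after the inclusion of the first patient".

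Protocol XVI (Phase III step) has the same error rate, power and 130 deaths, but a different monitoring plan: "Two interim analyses are planned to reject H0 or H1". The first look is at about 10 deaths (8%), at the final phase II analysis. The second is at 80 deaths, described as two thirds of the total, 34 months after the first inclusion. The protocol names East, Lan-DeMets spending and O'Brien-Fleming, and prints no p thresholds.

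**The concern.** The SAP table holds the only numeric rejection thresholds for the primary survival test. With an O'Brien-type boundary and one look at half the information, little alpha is used early, and the final nominal level should stay close to 0.05. A final level of 0.0439 is too far below that. If it were applied as printed at 65 and 130 deaths, a final p between 0.0439 and 0.0479 would be declared negative although the 5% error allows a positive claim.

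The final-row power of 0.5811 sits beside a text that promises 90%. A reader could take it as the power of the trial.

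The documents also disagree on the number of looks, their timing and their purpose. Rejecting H1 at a look means stopping for futility, which the SAP does not provide for. Which looks spend alpha, and whether futility stopping is allowed, is therefore not settled.

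**Working it through.** **Inputs.** Two-sided alpha 0.05, 90% power, looks at 65 and 130 deaths, nominal p 0.0054 and 0.0439 (SAP 5.5.3); 2-year survival 40% and 60%, 180 patients, uniform 24-month inclusion (SAP 5.5.3, protocol XVI); 1:1 allocation (protocol summary).

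**1. Does the printed pair use 5%?** The two logrank statistics are bivariate normal with correlation √(65/130) = √0.5. The two-sided p values correspond to z₁ = 2.782 and z₂ = 2.015.

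- Overall error: 1 − P(|Z₁| < 2.782, |Z₂| < 2.015) = **0.0461**.
- Keeping 0.0054 and solving for the final z that gives 0.0500: z₂ = 1.979, so final p = **0.0479**.
- Check without integration: the overall error cannot exceed the sum of the nominal levels, 0.0054 + 0.0439 = 0.0493. The pair cannot use 5% at any information fraction.
- An interim level of about 0.0120 would be needed to pair with 0.0439 at half information.

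**2. What do O'Brien-type rules give at 65/130?** The Lan-DeMets form on the two-sided 5% spends 2[1 − Φ(1.96/√t)], which is 0.00557 at t = 0.5.

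| Rule | Interim p | Final p |
|---|---|---|
| Lan-DeMets on two-sided 5% | 0.0056 | 0.0478 |
| Classical O'Brien-Fleming | 0.0052 | 0.0480 |
| Lan-DeMets, 2.5% per side | 0.0031 | 0.0490 |
| SAP table | 0.0054 | 0.0439 |

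The SAP's interim level is close to the first two rules. Its final level is close to none.

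**3. Power.** The drift for 90% power at two-sided 5% is 1.960 + 1.282 = 3.2415 (unrounded sum). The mean of Z₁ is 3.2415 × √0.5 = 2.292, so interim power at 0.0054 is 1 − Φ(2.782 − 2.292) = 0.312.

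| Pair | Interim | Added at final | Cumulative |
|---|---|---|---|
| 0.0054 / 0.0439 | 0.3120 | 0.5792 | 0.8913 |
| 0.0054 / 0.0479 | 0.3120 | 0.5858 | 0.8978 |
| 0.0056 / 0.0478 | 0.3157 | 0.5820 | 0.8977 |
| SAP, printed | 0.3156 | 0.5811 | (sum) 0.8967 |

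The SAP's 0.5811 is therefore the increment at the final look. The best match to its interim power of 0.3156 is the Lan-DeMets rule on the two-sided 5%; the rule at 2.5% per side gives only 0.25.

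**4. Where might 0.0439 come from?** This is inference; the documents do not say.

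- It may be alpha spent at the final look, entered in a column headed nominal p. Lan-DeMets on the two-sided 5% spends 0.0056 and then 0.0500 − 0.0056 = 0.0444. With its power increments of 0.3157 and 0.5820, all four printed cells fit within 0.001. If 0.0439 is the alpha spent after 0.0054, the final nominal level is 0.0472 and cumulative power is 0.8967.
- It may be the final level for one look at two thirds of the information under the same function, which is 0.04395.

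**5. Are the two look schedules the same within rounding?** With exponential survival, the monthly hazards are −ln(0.4)/24 and −ln(0.6)/24. For 90 patients per arm included uniformly over 24 months, expected deaths are 10.1 at 10 months, 64.7 at 28 months and 82.8 at 34 months. Each document's timing agrees with its own death count, so these are different looks: 80 − 65 = 15 deaths apart as planned, and 82.8 − 64.7 = 18.1 apart as computed.

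**6. The protocol's fraction.** 80/130 = 61.5%, while 2/3 × 130 = 86.7, that is 87 deaths, expected at about 36 months. The 34-month date fits 80 deaths, so the fraction looks like the slip.

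**The case against.** The strongest reply is that the design is sound and only a column is mislabelled. The cells fit alpha spent per look better than nominal p. If the planned maximum is taken as 130.8 deaths instead of 130 (an assumption; the SAP prints 130), Lan-DeMets spending on the two-sided 5% gives 0.0054 and 0.0439 to four decimals, though the power cells then come out as 0.3133 and 0.5838 and do not match. This may well be the origin. It does not rescue the table: the column is headed nominal p, and a statistician who uses it that way applies the wrong final level.

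Second, the SAP promises to recompute the levels from actual event counts, and 5.6.3.2 places the final analysis only approximately at the 130th death. A proper re-run would replace 0.0439. That limits the practical harm, but the adjustment is meant for counts that miss the plan, and the printed value is wrong at exactly 65 and 130. A re-run also needs to know which O'Brien-type function applies and whether alpha is spent per side, and the SAP does not say.

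Third, the power column does not claim to be cumulative. That is fair. The 0.5811 is a presentation fault and not a loss of power.

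Fourth, the schedule conflict may reflect document versions. SAP 5.6.1 and 5.7.1 rely on protocol Amendment 3, and the liver-failure definition in SAP 5.7.1 differs from that in protocol XII, so the protocol supplied may not be the one the SAP implements. That is possible. However, those references concern the pilot phase and the toxicity endpoint, and neither document records a change to the interim plan.

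**Conclusion.** The point holds. At 65 and 130 deaths, 0.0054 and 0.0439 read as nominal two-sided levels give an overall error of 0.0461, and the final level that pairs with 0.0054 is 0.0479. The error is on the safe side. Its cost is about 0.7 points of cumulative power (89.1% against 89.8% at the 90% drift) and a zone of final p values from 0.0439 to 0.0479 that would wrongly be called negative. The critical hazard ratio at 130 deaths, exp(−2z/√130), moves only from 0.707 to 0.702. The final power entry is an increment, and cumulative power agrees with the stated 90%.

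The conflict over looks is the more open matter: two looks that may reject either hypothesis against one superiority look, with the later looks 6 months apart. These results assume the usual joint normality of the logrank statistics and, for the timing, exponential survival with uniform inclusion and no dropout among 180 patients. The source of 0.0439 cannot be determined from the documents. It should be fixed, but it does not threaten the validity of the design.

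**What to change.** In SAP 5.5.3:

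- Name the spending function exactly and say whether alpha is spent on the two-sided 5% or at 2.5% per side.
- Print a matched nominal pair for 65 and 130 deaths: 0.0056/0.0478 for Lan-DeMets on the two-sided 5%, which best fits the printed interim power; 0.0054/0.0479 if the interim level is kept; or 0.0031/0.0490 if 2.5% per side is meant.
- Put alpha spent in its own column, apart from nominal p, and show cumulative power (about 0.90) in the final row.

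Across the documents, before any interim survival data are seen:

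- Settle one schedule of looks and one purpose (superiority only, or futility as well). If an amendment already changed the protocol's plan, cite it in the SAP.
- If the protocol's second look stays, correct the two-thirds fraction to 61.5% or the death count to 87.

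The cost is a re-run of the boundary software and text corrections in both documents. The 130 deaths and the number of patients stay as they are.

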5.6 Stages of the test

5.6.1 Pilot phase

During the pilot phase, 10 chemoembolizations (8 patients included) were performed with sunitinib. Of these 10 chemoembolizations, less than 4 toxicities were retained for the primary endpoint (see protocol, Amendment 3), the trial continued in randomized phase II. **Patients included in the pilot phase are not included in la phase II.**

The pilot phase was the subject of a specific report which was sent to the ANSM for information

5.6.2 Phase II

At the end of the 35 patients/arm inclusions of the phase II:

- if the number of patients with severe toxicity (liver failure, bleeding) in the sunitinib arm is less than or equal to 7, the trial will be continued in phase III;
- if the number of patients with severe toxicity (liver failure, bleeding) in the sunitinib arm is greater than or equal to 8, the number of complications (liver failure, bleeding) in the placebo arm should also be considered:
 - if the complication rate (liver failure, bleeding) in the placebo arm is greater than or equal to 8, an independent committee of experts will have to judge the appropriateness of continuing the trial in phase III since the toxicity in the sunitinib arm may be related to the "background noise" of the toxicity of chemoembolization alone;
 - if the complication rate (liver failure, bleeding) in the placebo arm is less than or equal to 7, the independent expert committee will have to judge whether to stop the trial.

The decision rules will apply only to the sunitinib/chimio/embolization arm; the placebo/chimio/embolization arm will be maintained in all cases for la phase III, if it occurs, with this arm serving as the control arm.

5.6.3 Phase III

This step will only be performed if the trial has not been stopped at the end of la Phase II.

5.6.3.1 Intermediate Analysis

An interim analysis at 65 deaths is planned. This may provide early evidence of superiority of the sunitinib arm.

5.6.3.2 Final Analysis

The final analysis will be done at approximately the 130th event (death), after inclusion of all 180 patients and a minimum follow-up for the last included patient of 3 years.

